# 6 Trial Treatment

# 6.1 Trial Treatment(s) Administered

Trial treatment may refer to the following compounds, either:

- 1. BNT411, and/or
- 2. Atezolizumab, and/or
- 3. Carboplatin, and/or
- 4. Etoposide.

BNT411 is a highly potent and selective small molecule TLR7 agonist of the imidazoquinoline family being developed by BioNTech and is a new investigational agent to be tested clinically in this trial. In all countries participating in the trial, BNT411 is considered as investigational medicinal product (IMP).

Atezolizumab is a PD-L1 blocking antibody indicated for the treatment of patients with various cancer diagnoses at different stages. Atezolizumab was first approved by FDA on May 18, 2016 to treat urothelial carcinoma, and similar positive opinion by European Medicines Agency (EMA) followed in July 2017. Carboplatin is a platinum coordination compound and etoposide is a topoisomerase inhibitor. They are both cytotoxic agents used in various chemotherapy regimens to treat many cancer indications. On March 18, 2019, the FDA approved atezolizumab in combination with carboplatin and etoposide, for the first-line treatment of adult patients with ES-SCLC. Since then, it has become a standard-of-care treatment in the US. In October 2019, EMA issued similar positive opinion for the combination. For the purpose of this trial, in the USA and UK, atezolizumab, carboplatin and etoposide are considered as non-investigational medicinal products (NIMPs). However, the individual drugs are considered as IMPs in Spain and Germany at the request of the competent authorities due to their use in combination with BNT411.

Information relating to COVID-19 vaccinations including a risk-benefit assessment and guidance for vaccination during this clinical trial is provided in Sections 10.8 and 10.9.

# 6.1.1 BNT411

In Part 1A, BNT411 will be administered using a 100 mL intravenous infusion on Days 1, 8 and 15 of each 3-week treatment cycle (21 days) of the first 4 cycles after all required procedures and assessments have been completed. In the following cycles thereafter, BNT411 will be administered every 3 weeks on Day 1 of each 3-week treatment cycle (21 days) after all required procedures and assessments have been completed.

In Part 1B, BNT411 will be administered using a 100 mL intravenous infusion on Days 2, 8 and 15 of each 3-week treatment cycle (21 days) of the first 4 cycles after all required procedures and assessments have been completed. In the following cycles thereafter, BNT411 will be administered every 3 weeks on Day 2 of each 3-week treatment cycle (21 days) after all required procedures and assessments have been completed.

In both Part 1A and Part 1B, patients will be administered BNT411 according to dose levels outlined in Table 4-2. BNT411 will be administered as a body weight-based dosing. A cap on dosing for patients weighing 120 kg and more will be implemented in the proposed clinical trial.

In Part 1B, for combination with atezolizumab and chemotherapy, the administration will be in the following order:

Day 1: Atezolizumab → Carboplatin → Etoposide

Day 2: **BNT411** → Etoposide

Day 3: Etoposide

For each dosing of BNT411 in Cycle 1, patients will remain in the treatment center and be closely monitored for immediate AEs for at least 6 hours. Hospitalization is required for the first 24 hours after the first BNT411 administration in Cycle 1 for clinical observation and PK sampling. Prolongation of the hospitalization beyond 24 hours may be performed at the investigator's discretion if deemed necessary based on potential risks related to the trial treatment and clinical status of the patient. For each subsequent dose of BNT411 in all cycles, patients will be monitored for at least 6 hours.

# 6.1.2 Atezolizumab, Carboplatin, and Etoposide

Atezolizumab, carboplatin, and etoposide will be used in the commercially available formulation.

For information on the formulation, packaging, and handling of atezolizumab, carboplatin, and etoposide, see the prescribing information for each drug.

The recommended dosage of atezolizumab is 1200 mg intravenously over 60 minutes every 3 weeks. If the first infusion of atezolizumab is tolerated, all subsequent infusions may be delivered over 30 minutes.

Carboplatin should be administered after completion of atezolizumab by intravenous infusion over 30–60 minutes to achieve an initial target AUC of 5 mg/mL/min (Calvert formula dosing) with standard anti-emetics per local practice guidelines. Because of their immune-suppressive effect, premedication with corticosteroids should be minimized to the extent that is clinically feasible.

On Day 1 of each cycle, etoposide ( $100 \text{ mg/m}^2$ ) should be administered intravenously over 60 minutes following carboplatin administration. The dose will be calculated using the Mosteller formula (BSA [ $m^2$ ] = square root((height [cm] x weight [kg])/3600))

On Day 2 and Day 3 of each cycle, etoposide (100 mg/m²) should be administered intravenously over 60 minutes. Premedication should be administered according to local standard-of-care. Because of their immune-suppressive effect, premedication with corticosteroids should be minimized to the extent that is clinically feasible.

After the DLT-observation period, if the patient tolerates the combination of atezolizumab+carboplatin+etoposide+BNT411, chemotherapy should continue for a total of 4 cycles; further chemotherapy cycles at the investigator's discretion should be discussed with the Medical Monitor. After completion of chemotherapy, atezolizumab+BNT411 combination should continue until one of the protocol-defined treatment discontinuation criteria is met (Section 7.1).

For the dosing schedule, refer to the Schedule of Activities (SoA), Section 1.3.

# 6.2 Preparation/Handling/Storage/Accountability

- 1. The investigator or designee must confirm appropriate temperature conditions have been maintained during transit for all trial treatment received and any discrepancies are reported and resolved before use of the trial treatment.
- 2. Only patients enrolled in the trial may receive trial treatment and only authorized site staff are allowed to supply or administer trial treatment. All trial treatment must be stored in a secure, environmentally controlled, and monitored (manual or automated) area in accordance with the labeled storage conditions with access limited to the investigator and authorized site staff.
- 3. Details regarding trial medication preparation are provided in the Pharmacy Manual.
- 4. The investigator or designee, institution, or the head of the medical institution (where applicable) is responsible for trial treatment accountability, reconciliation, and record maintenance (i.e. receipt, reconciliation, and final disposition records).
- 5. Further guidance and information for the final disposition of unused trial treatments are provided in the Pharmacy Manual.

# 6.3 Measures to Minimize Bias: Randomization and Blinding

Not applicable as this is a non-randomized, open-label trial.

# **6.4** Trial Treatment Compliance

When patients are dosed at the site, they will receive trial treatment directly from the investigator or designee, under medical supervision. The date and time of each dose administered in the clinic will be recorded in the source documents and the eCRF. The dose of trial treatment and trial patient identification will be confirmed at the time of dosing by a member of the trial site staff other than the person administering the trial treatment.

# 6.5 Concomitant Therapy and Procedures

Any medication or vaccine (including over-the-counter or prescription medicines, vitamins, and/or herbal supplements) or procedure that the patient is receiving or undergoing at the time of signing the Informed Consent Form, or receives or undergoes during the trial must be recorded along with, as applicable:

- reason for use
- dates of administration including start and end dates
- dosage information including dose and frequency.

The Medical Monitor should be contacted if there are any questions regarding concomitant or prior therapy.

Concomitant anti-emetics, anti-diarrheal agents, intravenous fluids, or electrolyte replacement based on clinical or laboratory assessments and blood transfusions while on treatment based on individual institutional guidelines will be allowed.

Radiotherapy should be documented in the eCRF including total dose, fractionation and location. The prohibited medications while on trial treatment are as follows:

- Other anti-cancer therapy not included under trial treatment in a given part of the trial (e.g. Part 1A, Part 1B and Part 2).
- Other prohibited concomitant medications as listed in inclusion and exclusion criteria (Section 5.1 and Section 5.2).
- No systemic anti-cancer therapies should be administered concurrently with PCI. A delay of ≤21 days in administering systemic anti-cancer therapies due to PCI is not considered a protocol deviation.
- For further guidance on prohibited and restricted medications, please refer to the IB for BNT411, and USPI or SmPCs for atezolizumab, carboplatin and etoposide.

#### 6.5.1 Premedication

As part of its intended mode of action, BNT411 is expected to induce a discrete spectrum of cytokines. These may be associated with flu-like symptoms within the first hours after administration.

Routine premedication with analgesics or anti-pyretics such as acetaminophen/paracetamol, ibuprofen, naproxen, or aspirin at established doses and schedules can be given at the investigator's discretion and patients can be appropriately prehydrated prior to treatment.

Because of their immune-suppressive effect, premedication with corticosteroids should be minimized to the extent that is clinically feasible. The use of corticosteroids as anti-emetics or for any other purposes may be substituted with other drugs from different classes per investigator's discretion. All premedication must be reported on the concomitant medication page in the eCRF.

#### **6.5.2** Rescue Medication

Not applicable.

#### 6.6 Dose Modifications

#### **Dose Limiting Toxicity**

In general, a DLT for a drug or other treatment is defined as an adverse event that prevents an increase of the dose level of that treatment (for details on reporting see Section 8.7.8).

For the purpose of dose escalation, the DLT monitoring period will be 21 days. The occurrence of any of the toxicities outlined in this section will be considered a DLT, excluding toxicities clearly related to disease progression or intercurrent illness.

SAEs, non-serious (NS) Grade  $\geq 3$  AEs and clinically significant abnormal laboratory values Grade  $\geq 3$  will be collected and assessed for DLTs (for each dose level during the first cycle). NCI CTCAE v.5.0 will be used to grade the intensity of AEs.

No indications of organ-specific autoimmunity have been identified for BNT411, or for any other imidazoquinoline compounds. Therefore, the risk of immune-related AEs (irAEs) with BNT411 alone is regarded as low. BNT411 will be combined with atezolizumab in Part 1B of

the dose escalation. At ezolizumab in line with its mode-of-action is associated with organspecific autoimmunity and consequently with immune-related adverse events.

Therefore, definitions of DLT will be categorized as non-immune-related AEs and immune-related AEs (irAEs).

Other clinically significant toxicities, including a single event or multiple occurrences of the same event, may be considered as DLTs.

AEs occurring after treatment Cycle 1 may be considered DLTs upon discussion between the investigator(s) and the sponsor(s) medical monitor.

Any other toxicity assessed as related to BNT411 treatment, and which in the opinion of the trial investigator(s) and the sponsor(s) medical monitor constitutes a DLT.

#### **Dose-escalation:**

Patients experiencing a DLT (an AE fulfilling the DLT criteria within the DLT period of 21 days) should discontinue trial drug immediately. If requested by the investigator, the sponsor may allow a patient with a DLT to continue in the trial and consider a reduced dose. For this decision, a thorough benefit-risk assessment of the individual patient is required and consultation with the SRC needs to be considered.

#### 6.6.1 Dose Limiting Toxicity for Part 1A

#### Non-immune-related AEs that are considered DLTs:

During the first treatment cycle, any toxicity that is of Grade 3 and that does not resolve to Grade 1 or lower within a week despite the use of medical intervention, or that is of Grade 4, but with exceptions as follows:

- The following events occurring during the DLT period ARE also considered a DLT:
  - o Arrhythmia: Grade >2 newly developed arrhythmia of any kind.
  - Absolute leucocyte count  $\geq 50 \times 10^9$ /L sustained for 14 days.
  - Hypotension of Grade 3 that persists for >4 hours and requires hospitalization.
- The following events occurring during the DLT period ARE **NOT** considered a DLT:
  - o Grade <3 nausea or vomiting controllable with anti-emetics within 72 hours.
  - Hypotension (systolic pressure <90 mm Hg) of Grade <3 that is of limited duration (less than 72 hours) or can be managed with hydration measures.
  - o Hypotension that requires a precautionary admission for observation after Grade 3 hypotension that persists for ≤4 hours.
  - o Grade 3 amylase and lipase elevations that are not accompanied by clinical signs/symptoms of pancreatitis.

#### Immune-related AEs that are considered DLTs:

- Any Grade 4 irAEs regardless of duration.
- Grade 3 colitis that does not downgrade to Grade ≤2 within 3 days after onset of the event despite maximal supportive care including systemic corticosteroids or downgrade to Grade <1 or baseline within 14 days.
- Any Grade 3 or Grade 4 non-infectious pneumonitis regardless of duration.

- Any Grade 3 irAE, excluding colitis and pneumonitis, that does not downgrade to Grade ≤2 within 3 days after onset of the event despite maximal supportive care including systemic corticosteroids or downgrade to Grade ≤1 or baseline within 14 days.
- Any Grade 2 pneumonitis that does not resolve to Grade ≤1 within 3 days of the initiation of maximal supportive care.
- Liver transaminase elevation higher than 8×ULN or total bilirubin higher than 3×ULN.
- Any other toxicity that is greater than baseline grade, is clinically significant and/or unacceptable, and is judged to be a DLT by the investigator and the sponsor.
- The definition excludes the following conditions:
  - o Grade ≤4 lymphopenia which is not considered clinically significant by the investigator.
  - o Grade 3 endocrinopathy that is managed with or without systemic corticosteroid therapy and/or hormone replacement therapy and the patient is asymptomatic.
  - o Grade 3 inflammatory reaction attributed to a local anti-tumor response (e.g. inflammatory reaction at sites of metastatic disease, lymph nodes) that resolves to Grade ≤1 within 3 weeks.
  - o Concurrent vitiligo or alopecia of any AE grade.

# 6.6.2 Dose Limiting Toxicity for Part 1B

#### Non-immune-related AEs that are considered DLTs:

During the first treatment cycle, any toxicity that is of Grade 3 and that does not resolve to Grade 1 or lower within a week despite the use of medical intervention, or that is of Grade 4, but with exceptions as follows:

- The following events occurring during the DLT period ARE also considered a DLT:
  - Arrhythmia: Grade >2 newly developed arrhythmia of any kind.
  - Absolute leucocyte count >50×10^9/L sustained for 14 days.
  - Hypotension of Grade 3 that persists for >4 hours and requires hospitalization.
- The following events occurring during the DLT period ARE NOT considered a DLT:
  - o Any Grade 3 or 4 neutropenia, leucopenia, anemia and thrombocytopenia that can be solely attributed to chemotherapy compounds.
  - o Grade ≤3 nausea or vomiting controllable with anti-emetics within 72 hours.
  - Hypotension (systolic pressure <90 mm Hg) of Grade <3 that is of limited duration (less than 72 hours) or can be managed with hydration measures.
  - Hypotension that requires a precautionary admission for observation after Grade 3 hypotension that persists for ≤4 hours.
  - o Grade 3 amylase and lipase elevations that are not accompanied by clinical signs/symptoms of pancreatitis.

#### Immune-related AEs that are considered DLTs:

- Any Grade 4 irAEs regardless of duration.
- Grade 3 colitis that does not downgrade to Grade ≤2 within 3 days after onset of the event despite maximal supportive care including systemic corticosteroids or downgrade to Grade ≤1 or baseline within 14 days.
- Any Grade 3 or Grade 4 non-infectious pneumonitis regardless of duration.

- Any Grade 3 irAEs, excluding colitis and pneumonitis, that does not downgrade to Grade ≤2 within 3 days after onset of the event despite maximal supportive care including systemic corticosteroids or downgrade to Grade ≤1 or baseline within 14 days.
- Any Grade 2 pneumonitis that does not resolve to Grade ≤1 within 3 days of the initiation of maximal supportive care.
- Liver transaminase elevation higher than 8×ULN or total bilirubin higher than 3×ULN.
- Any other toxicity that is greater than baseline grade, is clinically significant and/or unacceptable, and is judged to be a DLT by the investigator and the sponsor.
- The definition excludes the following conditions:
  - o Grade ≤4 lymphopenia which is not considered clinically significant by the investigator.
  - o Grade 3 endocrinopathy that is managed with or without systemic corticosteroid therapy and/or hormone replacement therapy and the patient is asymptomatic.
  - ⊙ Grade 3 inflammatory reaction attributed to a local anti-tumor response (e.g. inflammatory reaction at sites of metastatic disease, lymph nodes) that resolves to Grade ≤1 within 3 weeks.
  - o Concurrent vitiligo or alopecia of any AE grade.

[figure not shown]
## 6.6.3 Dose Modification Guidance

# 6.6.3.1 Handling of Adverse Events Fulfilling the DLT Criteria after the DLT Period has ended in Part 1A

AEs that fulfill the DLT criteria after the DLT period has ended in the dose-escalation phase of Part 1A of the trial (i.e. from Cycle 2 Day 1 and beyond) or during the expansion phase (i.e. from Cycle 1 Day 1 and beyond) should be handled as shown in Figure 6-1.

Please Note: Patients must complete the DLT monitoring period prior to implementing the dose modification criteria outlined in this section.

Figure 6-1: Handling of adverse events fulfilling the DLT criteria after the DLT-observation period has ended – Part 1A

DL, dose level

\*Dose delay: Next dose of BNT411 can maximally be delayed 21 days unless approved otherwise by the sponsor medical monitor.

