## 4.1.1 Dose Escalation (Part 1A and 1B)

#### 4.1.1.1 Dose Escalation in Part 1A

The dose escalation starts with an accelerated phase consisting of single patient cohorts followed by larger patient cohorts informed by a classical 3+3 design. The single patient cohorts in the first 3 dose levels will be expanded to 3+3-patient cohorts in case of occurrence of Grade ≥2 toxicities, or the occurrence of DLTs, or based on the decision of the sponsor's SRC based on safety data generated. In addition, in the single-patient cohort phase, the next cohort can only start once the DLT period for the previous dose level has been assessed and the next dose level is proposed by the SRC and endorsed by the sponsor. Once a single-patient cohort has been expanded, all future cohorts will follow the 3+3 design. Additional details regarding the SRC can be found in Section 9.6. The DLT period is defined as one cycle (i.e. 21 days).

During the 3+3 phase, at every dose level to be tested, staggered enrollment will be employed as described below. In each dose level cohort, the 3 patients will be dosed successively with a safety monitoring interval of at least 48 hours between the intravenous administration of BNT411 in the first and the second patient, and between the second and the third patient. The safety monitoring period is reduced to at least 24 hours when expanding a dose level which has already been declared safe.

Hospitalization is required for the first 24 hours after the first BNT411 administration in Cycle 1 for clinical observation and PK sampling. Prolongation of the hospitalization beyond 24 hours may be performed at the investigator's discretion if deemed necessary based on potential risks related to the trial treatment and clinical status of the patient. For the assessments of each cohort, the dose limiting toxicities will be collected for the first treatment cycle, i.e., a DLT evaluation period of 21 days.

Dose escalation will follow a classical 3+3 design and continue until DLTs are observed in 2/3 or 2/6 patients as described in the following dose escalation table (Table 4-1).

**Table 4-1:** Dose escalation table

Number of evaluable patients with DLT at a given dose level after the first treatment cycle	Escalation decision rule
0 out of 3 OR 1 out of 6	Enter patients at the next higher dose level
1 out of 3	Enter more patients at this dose level to a total of at least 6 evaluable patients or 2 patients with DLT

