2 out of 3 OR at least 2 out of 6	Dose escalation will be stopped, the MTD will be considered to be reached at the one before the last dose level explored. The sponsor will decide, based on a discussion between the investigators and the sponsor at a dose escalation meeting, if additional patients need to be enrolled and at which dose to finalize the trial
Any condition which would require further clarification of safety	A cohort of 6 patients can eventually be extended and more patients can be enrolled in a cohort if decided by the sponsor based on a discussion between the investigators and the sponsor at a dose escalation meeting

DLT = dose-limiting toxicity; MTD = maximal tolerated dose.

The dose escalation will potentially (dependent on data collected during the trial) evaluate BNT411 at eight main dose levels as shown in Table 4-2.

Dose Level	Dose of BNT411* (μg/kg/administration)	Dose Increment*
1**	0.05	Starting dose
2**	0.15	200%
3**	0.45	200%
4	1.2	166%
5	2.4	100%
6	4.8	100%
7	9.6	100%
8	16.0	66%

**Table 4-2:** BNT411 dose increments

Based on the nonclinical toxicology profile, which does not suggest a steep dose- or exposure-response curve and showed no severe toxicity findings, an initial dose tripling is proposed. Subsequently, standard dose doubling is proposed starting from dose level 4 in line with the FDA Guidance for Industry S9 Nonclinical Evaluation for Anticancer Pharmaceuticals. Based on nonclinical data, dose level 4 is the anticipated minimal efficacious dose. Furthermore, the sponsor proposes seven optional, intermediate dose levels at 0.075, 0.225, 0.9, 1.8, 3.6, 7.2 and  $12.8 \,\mu g/kg$ .

To be eligible for DLT assessment, patients should receive all three infusions of BNT411 during Cycle 1 (DLT assessment period). Patients who will not be able to fulfil the criteria for the DLT assessment will be replaced and this only applies to patients who do not experience a DLT. As long as patients do not experience a DLT, patients who have been replaced can continue with BNT411 treatment and follow the same trial procedures until unacceptable toxicity, documented disease progression, and/or the onset of a new anti-cancer therapy (palliative radiotherapy of, for example, painful bone metastases not defined as target lesions will be allowed).

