After completion of the DLT period for each cohort, the SRC will review the data from the DLT period – including but not limited to all relevant safety and clinical data – to propose a dose level for the next cohort of patients; PK and pharmacodynamics data, if available, will also be taken into consideration.

The sponsor can backfill a certain dose level cohort to explore and generate more safety, PK, pharmacodynamics, and anti-tumor data up to a total of 14 patients in a given cohort. Staggering would not be implemented as backfilling would occur once the dose level is declared safe by the SRC.

\* Can be reduced or increased as a function of the observed biologic activity and based on other data generated during the trial for dose optimization.

\*\* Accelerated titration (single patient cohorts). Will be expanded to 3+3-patient cohorts in case of occurrence of Grade ≥2 toxicities, or the occurrence of DLTs, or based on the decision of the sponsor's SRC based on safety data generated.

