## 4.4 Dose and Schedule Rationale

Administration of TLR7 agonists results in the activation of pDCs followed by their transient depletion. Consequently, the pool of excitable pDCs has to be replenished by expanding and maturing precursor cells from the bone marrow (Markov et al, 2016), a process which takes about 7 days (Bourquin et al, 2011; Tsitoura et al, 2015). It has been described for other TLR7 agonists that this may result in tachyphylaxis, meaning that within this time period, additional administrations will not result in further secretion of IFN $\alpha$  (Bourquin et al, 2011; Tsitoura et al, 2015). To avoid this mechanism and yet ensure frequent stimulation of the immune system, BNT411 will be administered once weekly in the first 4 cycles. These 4 cycles are considered to induce a sufficient immune response. Consequently, BNT411 is applied every 3 weeks as a maintenance therapy after the first 4 cycles instead of every week.

BNT411 will be administered as a 30-minute infusion in the clinic. Preclinical experiments revealed acute adverse effects at lower doses when administered as bolus injection but not as infusion, while pharmacodynamic parameters remained comparable, irrespectively of the duration of compound administration.

The BNT411 starting dose of  $0.05 \mu g/kg$  is calculated based on a minimally anticipated biologic effect level (MABEL) approach with an additional safety factor of 25:

- Upon BNT411 exposure, IFNα-secretion is the earliest detectable pharmacodynamics marker in human whole blood preparations.
- 4 nM is the minimal effective concentration (MEC) of BNT411 needed to induce IFN $\alpha$  in this *in vitro* setting (Studies R-19-0027 and R-19-0028), which equals approximately a human plasma  $C_{max}$  of 2 ng/mL.
- To reach this target plasma concentration, an intravenously applied dose of 1.25 μg/kg is required (based on human pharmacokinetic modeling with animal data; Study BNSM2018002). This dose equals approximately dose level 4 (1.2 μg/kg).
- A safety factor of 25 is applied, resulting in the proposed human starting dose of 0.05 μg/kg.

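### The 3-day window either side of Cycle 2 Day 1 allows Cycle 2 dosing on Days 19-21, inside the 21-day DLT period

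*Protocol*

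**What the plan says.** Protocol Section 4.1.1.1: "The DLT period is defined as one cycle (i.e. 21 days". Section 6.6 repeats this ("For the purpose of dose escalation, the DLT monitoring period will be 21 days") and, for the individual patient, describes a DLT as "an AE fulfilling the DLT criteria within the DLT period of 21 days". Section 9.3 and SAP Section 7.1 require a patient without a DLT to be observed for at least 21 days after the first dose and to have a Cycle 1 relative dose intensity (RDI) of 100%.

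Sections 6.6.3.1 and 6.6.3.2 place Cycle 2 Day 1 after the DLT period. In Part 1A their rules for later events apply "in the dose-escalation phase of Part 1A of the trial (i.e. from Cycle 2 Day 1 and beyond". For Part 1B, Section 6.1.2 opens the sentence on continuing chemotherapy with "After the DLT-observation period, if the patient tolerates the combination of".

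The schedule tables (Protocol Tables 1-1 and 1-2, SAP Tables 5 and 6) give Day 1 of Cycles 1-2 a window of 3 days either side, and Days 8 and 15 a window of 1 day either side. In Part 1A, BNT411 is given on Day 1. In Part 1B, the backbone (atezolizumab, carboplatin, etoposide) starts on Day 1 and BNT411 follows on Day 2, which has no window of its own.

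Table 4-1 sets the escalation rule. Escalation stops at "2 out of 3 OR at least 2 out of 6".

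**The concern.** The text assumes that Cycle 2 begins once DLT observation is over, but the visit window lets it begin earlier. No section gives an earliest day for Cycle 2 or a minimum interval between infusions.

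What is at stake is attribution. Each dose level is meant to be judged on the three infusions of Cycle 1. If a patient receives a fourth BNT411 infusion on Day 19 (Part 1A), or a second round of the backbone (Part 1B), and an event meeting the DLT criteria follows by Day 21, it still falls in the 21-day period and counts against that level. In cohorts of 3 to 6, one such event changes the decision. This is also a first-in-human trial, in which re-dosing before observation is complete is best avoided where it costs nothing to do so.

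**Working it through.** **Inputs.** Cycle and DLT period: 21 days (Protocol 4.1.1.1, 6.1.1). Day 1 window: 3 days either side; Day 15 window: 1 day either side (Tables 1-1 and 1-2). RDI formula: SAP 8.5.1. Assumption: windows are anchored to Cycle 1 Day 1 = Day 1; the documents do not state the anchor.

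**The plan's own figure.** 3 weeks × 7 = 21 days, so the DLT period is Days 1-21 and nominal Cycle 2 Day 1 is 1 + 21 = Day 22. This agrees with the text of 6.6.3.1.

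**Overlap.** The window runs from 22 − 3 = Day 19 to 22 + 3 = Day 25, which is 7 permitted days. Days 19, 20 and 21 are inside the DLT period: 3 of 7.
- Part 1A: BNT411 is given at this visit, so the fourth infusion can fall on any of the three days.
- Part 1B: the backbone can fall on any of the three. BNT411 follows a day later, on Day 20, 21 or 22, so it is inside the period for two of the three early starts.

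**Gap between third and fourth BNT411 infusions.**
- Part 1A: planned 22 − 15 = 7 days; shortest with an on-time third dose 19 − 15 = 4 days; with a Day 16 third dose 19 − 16 = 3 days.
- Part 1B: planned 23 − 15 = 8 days; shortest with an on-time third dose 20 − 15 = 5 days; with a Day 16 third dose 20 − 16 = 4 days.

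**Whether the shortest gaps concern DLT-evaluable patients.** With all doses given in full, RDI = planned duration ÷ actual duration.
- Part 1A: planned 15 − 1 + 7 = 21 days; with a Day 16 third dose, 16 − 1 + 7 = 22 days; RDI = 21/22 = 95.5%.
- Part 1B (SAP adds 8 days after a third dose): planned 15 − 2 + 8 = 21 days; with Day 16, 16 − 2 + 8 = 22 days; RDI again 95.5%.

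Both fail the 100% criterion, so such a patient is not evaluable unless a DLT occurs.

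**Effect on the escalation rule (Table 4-1).** One added event turns 0/3 (escalate) into 1/3 (expand), 1/3 (expand) into 2/3 (stop), or 1/6 (escalate) into 2/6 (stop).

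**Part 1B counting.** If the 21 days run from the first BNT411 dose on Day 2, they reach 2 + 21 = Day 23, compared with 1 + 21 = Day 22 in Part 1A. A Cycle 2 start on Day 22 would then also be too early, and 4 of the 7 permitted days (19-22) would overlap.

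**With a 0/+3 window.** Cycle 2 Day 1 falls on Days 22-25: 4 permitted days, none inside Days 1-21. Even after a Day 16 third dose, the shortest gaps become 22 − 16 = 6 days (Part 1A) and 23 − 16 = 7 days (Part 1B).

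**The case against.** The strongest reply is that the specific text already fixes the order. Dosing days are defined within 21-day cycles, the DLT period is one cycle, and 6.6.3 and 6.1.2 put Cycle 2 afterwards. On that view a generic window row is not permission to shorten the cycle, and its minus side may serve pre-dose assessments, some of which are allowed up to 3 days ahead. This is good evidence of intent. But the window applies to the visit at which dosing is marked, the table does not limit it to assessments, and 6.1.2 covers only the Part 1B chemotherapy. The missing Day 1 window in biomarker Table 1-7 governs samples, not treatment.

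A second reply is that Day 21 is not a sharp boundary. Section 6.6 lets events after Cycle 1 be considered DLTs on discussion, 4.1.1.2 allows the MTD to be lowered for serious related toxicity in later cycles, Table 4-1 allows a cohort to be extended, and "After completion of the DLT period for each cohort, the SRC will review the data from the DLT period", along with other relevant data. This stands, and it limits the harm. It does not remove the point: events up to Day 21 enter the count by rule, later ones only by judgment.

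Three stronger readings are tempting and should not be drawn.
- A reader might infer that DLTs are missed or that escalation becomes unsafe. The period is defined in days, so events to Day 21 still count, and the notes in 6.6.3.1 and 6.6.3.2 withhold the dose-modification rules until DLT monitoring is complete. The possible error is towards expanding or stopping.
- A reader might take Section 4.4 ("BNT411 will be administered once weekly in the first 4 cycles") as a toxicity argument against a short gap. It concerns tachyphylaxis: within about 7 days a further dose is expected to yield no further interferon-alpha. That supports the interval on pharmacodynamic grounds only.
- A reader might quote 3 days as the shortest gap in Part 1A. That requires a Day 16 third dose, which removes the patient from the evaluable set unless a DLT occurs.

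**Conclusion.** The point holds as an inconsistency between the schedule tables and the DLT definition. Three of the seven permitted days for Cycle 2 Day 1 lie inside the DLT period, and a qualifying event on those days after early Cycle 2 dosing would be charged to a dose level meant to be judged on three infusions. For a Part 1A patient dosed on time in Cycle 1, the fourth infusion can come 4 days after the third instead of 7.

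The consequence is modest. The bias is conservative, no DLT is lost, and the SRC sees all the data. The 3 of 7 counts permitted days and is not a probability; the documents do not say how often visits run early. The figures assume windows anchored to Cycle 1 Day 1 and, for Part 1B, a period counted by cycle (Days 1-21). If that period runs from the first BNT411 dose, the overlap is larger. The case for change rests on its low cost rather than on a demonstrated safety failure.

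**What to change.** - In Protocol Tables 1-1 and 1-2 and SAP Tables 5 and 6, set the Cycle 2 Day 1 window to 0/+3 days and add a footnote that Cycle 2 may not start before Day 22. The other Day 1 windows can stay.
- For Part 1B, state in Protocol Section 9.3 and SAP Section 7.1 that the 21 days are counted from Cycle 1 Day 1, the first dose of any trial treatment. If the sponsor instead counts from the first BNT411 dose on Day 2, set the earliest Part 1B Cycle 2 start to match (Day 23 on the count above).
- Sections 6.6.3.1 and 6.6.3.2 then agree with the 21-day period and need no edit.

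The cost is some scheduling flexibility at one visit, 4 permitted days instead of 7, plus a footnote per table and one clarifying sentence in each document. No patients, visits or data are added.
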